The signature below constitutes the approval of this protocol and the attachments, and provides the necessary assurances that this trial will be conducted according to all stipulations of the protocol, including all statements regarding confidentiality, and according to local legal and regulatory requirements and applicable U.S. federal regulations,⁴ ICH guidelines,² ISO 14155, and the Declaration of Helsinki.³

Study Responsible Clinician/Author	See Electronic Signature Report [name] Sr. Principal Research Optometrist	DATE
Clinical Operations Manager	See Electronic Signature Report [REDACTED] Manager, Clinical Operations	DATE
Biostatistician	See Electronic Signature Report [REDACTED] Senior Manager, Biostatistics	DATE
Data Management	See Electronic Signature Report [REDACTED] Clinical Project Mgr. Data & Systems	DATE
Reviewer	See Electronic Signature Report [REDACTED] Clinical Research Fellow	DATE
Approver	See Electronic Signature Report [REDACTED] Director - Global Sphere Platform	DATE

CHANGE HISTORY

Version	Originator	Description of Change(s) and Section Number(s) Affected	Date
1.0	[name]	Original Protocol	30 MAY 2018

SYNOPSIS

[figure not shown]
Protocol Title	Clinical Evaluation of etafilcon A Contact Lenses Using a Novel Molding Process
Sponsor	JJVC, [name]
Clinical Phase	Post Marketing, Phase 4
Trial Registration	This study will be registered on ClinicalTrials.gov by the Sponsor
Test Article(s)	
Investigational Products:
 
 • etafilcon A contact lenses made with a novel molding process (Test) • etafilcon A contact lenses made with the current molding process (Control).
Wear and Replacement Schedules	
Wear Schedule: daily wear
 
Replacement Schedule: daily

Objectives	To evaluate the clinical performance of etafilcon A lenses made with a novel molding process (Test) by comparison to etafilcon A lenses made with the current molding process (Control).
Study Endpoints	
Co-primary endpoint(s):
 
 • Overall comfort after 1-week of lens wear • Overall quality of vision after 1-week of lens wear 
Secondary endpoint(s):
 
 • Average daily wear time (in hour) • Monocular distance visual performance 
Additional Endpoints:
 
 • Slit lamp findings • Subject reported ocular symptoms • Lens fitting characteristics • Lens wettability • Adverse events
Study Design	
This study is a multi-site, group sequential, adaptive, randomized, double-masked, 2×2 crossover design, 1-week dispensing study. Subjects will wear bilaterally both Test and Control lenses in a random order for 1-week each as a daily disposable modality with a wash-out period of 1 week between the wearing periods.
 
See the flow chart at the end of the synopsis table for the schematic of the study visits and procedures of main observations (Figure 1).

Sample Size	In Phase 1, up to 160 eligible subjects will be enrolled and randomized into the study to ensure that approximately 150 subjects complete as cohort. An interim analysis will dictate if additional subjects will be enrolled in Phase 2 up to a maximum of 260.
Study Duration	For Phase 1, the study will last approximately 3 months and include an enrollment period of 3 weeks.
Anticipated Study Population	Healthy male and female volunteers (at least 18 and not more than 70 years old) who are habitual wearers of daily disposable contact lenses (approximately 80% 1-Day ACUVUE Moist, approximately 20% other daily disposable hydrogel contact lens brands) and have a spectacle astigmatism of $\leq 0.75\text{D}$ in both eyes.
Eligibility Criteria	
Potential subjects must satisfy all of the following criteria to be enrolled in the study:
 
Inclusion Criteria after Screening
 
 1. The subject must read, understand, and sign the STATEMENT OF INFORMED CONSENT and receive a fully executed copy of the form. 2. Appear able and willing to adhere to the instructions set forth in this clinical protocol. 3. Must be at least 18 and not more than 70 years of age (including 70) at the time of screening. 4. The subject must be a habitual and adapted wearer of hydrogel daily disposable brand contact lenses in both eyes (at least 1 month of daily wear). 5. The subject must have normal eyes (i.e., no ocular medications or infections of any type). 
Inclusion Criteria after Baseline
 
 6. The subject's required spherical contact lens prescription must be in the range of -1.00 to -4.50 D in each eye. 7. The subject's refractive cylinder must be $< 0.75\text{D}$ in each eye. 8. The subject must have best corrected visual acuity of 20/25 or better in each eye. 
Exclusion Criteria after Screening
 
Potential subjects who meet any of the following criteria will be excluded from participating in the study:
 
 1. Currently pregnant or lactating (subjects who become pregnant during the study will be discontinued).

	
 2. Any systemic disease, autoimmune disease, or use of medication that may interfere with contact lens wear. 3. Any previous, or planned, ocular or interocular surgery (e.g., radial keratotomy, PRK, LASIK, etc.). 4. Any ocular infection. 5. Any corneal distortion resulting from previous hard or rigid gas permeable contact lens wear. 6. Monovision or multi-focal contact lens correction. 7. Participation in any contact lens or lens care product clinical trial within 14 days prior to study enrollment. 8. History of binocular vision abnormality or strabismus. 9. Any infectious disease (e.g., hepatitis, tuberculosis) or a contagious immunosuppressive disease (e.g., HIV, by self-report). 10. Suspicion of or recent history of alcohol or substance abuse. 11. History of serious mental illness. 12. History of seizures. 13. Employee of investigational clinic (e.g., Investigator, Coordinator, Technician) 
Exclusion Criteria after Baseline
 
 14. Any ocular allergies, infections or other ocular abnormalities that are known to interfere with contact lens wear and/or participation in the study. This may include, but not be limited to entropion, ectropion, extrusions, chalazia, recurrent styes, glaucoma, history of recurrent corneal erosions, aphakia, or corneal distortion 15. Any Grade 3 or greater slit lamp findings (e.g., edema, corneal neovascularization, corneal staining, tarsal abnormalities, conjunctival injection) on the Food and Drug Administration (FDA) classification scale 16. Any previous history or signs of a contact lens-related corneal inflammatory event (e.g., past peripheral ulcer or round peripheral scar), or any other ocular abnormality that may contraindicate contact lens wear.
Disallowed Medications/Interventions	Disallowed medications include any medication that may interfere with contact lens wear (at the investigator's discretion).
Measurements and Procedures	Subjective assessments, physiological responses, fitting characteristics
Microbiology or Other Laboratory Testing	None

Study Termination	The occurrence of one or more Unanticipated Adverse Device Effect (UADE), or any SAE where relationship to study agent cannot be ruled out, will result in stopping further dispensing investigational product. In the event of a UADE or SAE, the Sponsor Medical Monitor may unmask the treatment regimen of subject(s) and may discuss this with the Principal Investigator before any further subjects are enrolled.
Ancillary Supplies/ Study-Specific Materials	Sterile rewetting drops
Principal Investigator(s) and Study Institution(s)/Site(s)	A full list of Principal Investigators, clinical sites, and institutions is kept separately from the Study Protocol and is included in the study Trial Master File.

Figure 1: Study Flowchart

COMMONLY USED ABBREVIATIONS AND DEFINITIONS OF TERMS

ADD	Plus Power Required For Near Use
ADE	Adverse Device Effect
AE	Adverse Event/Adverse Experience
BCVA	Best Corrected Visual Acuity
BSCVA	Best Spectacle Corrected Visual Acuity
CFR	Code of Federal Regulations
CLUE	Contact Lens User Experience
COAS	Complete Ophthalmic Analysis System
COM	Clinical Operations Manager
CRA	Clinical Research Associate
CRF	Case Report Form
CRO	Contract Research Organization
CT	Center Thickness
CTP	Clinical Technical Procedure
D	Diopter
DMC	Data Monitoring Committee
eCRF	Electronic Case Report Form
EDC	Electronic Data Capture
ETDRS	Early Treatment Diabetic Retinopathy Study
FDA	Food and Drug Administration
GCP	Good Clinical Practice
HIPAA	Health Insurance Portability and Accountability Act
IB	Investigator's Brochure
ICF	Informed Consent Form
ICH	International Conference on Harmonization
IDE	Investigational Device Exemption
IEC	Independent Ethics Committee
IRB	Institutional Review Board
ISO	International Organization for Standardization
ITT	Intent-to-Treat
JJVC	Johnson & Johnson Vision Care, Inc.
LC	Limbus Center
LogMAR	Logarithm of Minimal Angle of Resolution
MedDRA [®]	Medical Dictionary for Regulatory Activities
MOP	Manual of Procedures
NIH	National Institutes of Health
OD	Right Eye
OHRP	Office for Human Research Protections
OHSR	Office for Human Subjects Research
OS	Left Eye
OU	Both Eyes
PD	Protocol Deviation
PHI	Protected Health Information
PI	Principal Investigator
PIG	Patient Instruction Guide

PP	Predictive Probability
PQC	Product Quality Complaint
PRO	Patient Reported Outcome
QA	Quality Assurance
QC	Quality Control
SAE	Serious Adverse Event/Serious Adverse Experience
SAP	Statistical Analysis Plan
SAS	Statistical Analysis System
SD	Standard Deviation
SOP	Standard Operating Procedure
UADE	Unanticipated Adverse Device Effect
USADE	Unanticipated Serious Adverse Device Effect
VA	Visual Acuity

1. INTRODUCTION AND BACKGROUND

In the spirit of continuous improvement, JJVC has identified a potential process change in the how etafilcon A is manufactured, specifically in the base curve mold material. It is hypothesized that this process change may decrease lens defects, increase yields, and improve lens edge and optical quality. The purpose of this clinical trial is to demonstrate whether these process changes have any clinically relevant impact on the clinical performance of the contact lens.

1.1. Name and Descriptions of Investigational Products

The investigational products are:

- etafilcon A contact lenses made with a novel molding process (Test).
- etafilcon A contact lenses made with the current molding process (Control).

1.2. Intended Use of Investigational Products

The intended use of the investigative products is for correcting refractive error. During the study, each Test article will be worn bilaterally in daily wear, daily disposable modality for at least 8 hours per day for approximately 1 week.

1.3. Summary of Findings from Nonclinical Studies

All previous pre-clinical findings were deemed satisfactory prior to proceeding with clinical trials on humans. For the most comprehensive nonclinical information regarding etafilcon A refer to the latest version of the package insert for this study (APPENDIX C: PACKAGE INSERT (APPROVED PRODUCT)).

1.4. Summary of Known Risks and Benefits to Human Subjects

For the most comprehensive risk and benefit information regarding etafilcon A product refer to the latest version of the package insert (APPENDIX C: PACKAGE INSERT (APPROVED PRODUCT)).

1.5. Relevant Literature References and Prior Clinical Data Relevant to Proposed Clinical Study

See Package Inserts for 1-DAY ACUVUE® MOIST. (APPENDIX C: PACKAGE INSERT (APPROVED PRODUCT)).

2. STUDY OBJECTIVES, ENDPOINTS AND HYPOTHESES

2.1. Objectives

Primary Objective(s)

To evaluate the clinical performance of etafilcon A contact lenses made with a novel molding process by comparison to etafilcon A contact lenses made with the existing molding process in the following area:

- Overall comfort
- Overall quality of vision

Secondary Objective(s)

To evaluate the clinical performance of etafilcon A lenses made with a new molding process by comparison to etafilcon A lenses made with the existing molding process in the following area:

- Average daily wear time
- Monocular distance visual performance

2.2. Endpoints

Primary Endpoint(s)

CLUE Comfort and Vision Scores:

The co-primary endpoints for this study are subjective assessment of comfort and quality of vision after 7 ± 2 days of wearing the study lenses as a daily disposable.

Subjective assessment of comfort and vision will be performed using the Contact Lens User Experience™ (CLUE) questionnaire. CLUE is a validated patient reported outcomes (PRO) questionnaire used to assess patient experience attributes of soft contact lenses (comfort, vision, handling, and packaging) in a US contact-lens wearing population between 18 and 65 years of age. CLUE composite scores are derived using Item Response Theory (IRT) and follow a normal distribution with a population average score of 60 (SD 20), where higher scores indicate a more favorable/positive response. A 5-point increase in an average CLUE score translates into 10% shift in the distribution of scores for the population of soft disposable contact lens wearers.

Secondary Endpoint(s)

Average daily wear time (in hours):

Average daily wear time will be calculated as the number of hours between subjects reported time of insertion and time of removal of the study lenses, on an average day, at 1-Week Follow-up evaluation.

Visual performance

Visual performance will be calculated as monocular contact lens-corrected distance visual acuity using a logMAR visual acuity scale. This will be evaluated under high luminance and high contrast conditions at 4 meters from Early Treatment Diabetic Retinopathy Study (ETDRS) charts at the 1-Week Follow-up visit.

Other Endpoint(s)

Slit Lamp Findings

Frequency and severity by eye of slit lamp findings (SLFs) including conjunctival injection, corneal edema, corneal neovascularization, corneal staining, tarsal abnormalities or any other complications. SLFs will be evaluated at fitting and post-fitting evaluation visits including unscheduled visits.

Subject's Reported Ocular Symptoms

Frequency and severity by eye of subject's reported ocular symptoms and problems with the study lens at fitting and post-fitting evaluation visits including unscheduled visits.

Lens Fitting characteristics

Frequency by eye of mechanical lens fitting characteristics including lens centration and lens movement and overall lens fitting acceptability at fitting and 1-week follow-up evaluations.

Lens wettability:

Frequency and Grade by eye of lens wettability at 1-Week Follow-up evaluation.

The following will be monitored and descriptively evaluated

- Adverse events
- Reasons for discontinuation
- Lens damage

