4.3. Enrollment Target and Study Duration

This is a group sequential, adaptive design where the enrollment will be performed in two phases. In the first phase, up to 160 subjects will be initially enrolled and approximately 150 are targeted to complete the study. An interim analysis will be performed when all subjects have completed Phase 1. The interim analysis will be used to estimate if more subjects are needed. If needed, additional subjects will be added to the study, in phase 2, up to a maximum of 260.

The population to be studied will be healthy male and female volunteers (at least 18 and not more than 70 years old) who are habitual wearers of daily disposable (approximately 80% 1 Day ACUVUE MOIST, approximately 20% any other brand of hydrogel daily disposable contact lens) and have a spectacle astigmatism of <0.75 D in both eyes. Up to 165 subjects will be enrolled to ensure approximately 150 subjects successfully complete the study.

There will be a total of 4 visits and the study duration for Phase 1 will be approximately 3 months:

- Visit 1:** (Day 0): Baseline Screening and Initial Randomization/Dispensing Visit Treatment #1
- Visit 2:** (Day 5-9): 1-Week Follow-Up Visit with first pair of study lenses/Dispensing Visit Treatment #2
- Visit 3:** (Approximately 1 Week from Visit 2): Post wash-out baseline and Dispensing Visit for Treatment #2
- Visit 4:** (Day 5-9 from Visit 3): 1-Week Follow-up Visit with second pair of study lenses and study exit

The Investigator is responsible for ensuring that all subjects entering the study conform to subject selection criteria. The number of subjects targeted for randomization and completion are as follows:

Table 1: Target number of subjects by arm and phase

	Phase 1		Phase 2		All
	Test/Control	Control/Test	Test/Control	Control/Test	Total
Randomization	80	80	50	50	260
Completion	75	75	45	45	250
Number of sites					
Subjects/site (Min-Max)					

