2.6.	Visual Acuity	Record the distance Snellen visual acuity with the contact lenses (OD, OS, and OU) to the nearest letter. Subjects must read the smallest line until at least 50% of the letters are read incorrectly.	
2.7.	Distance ETDRS LogMAR Visual Acuity	
Perform monocular distance ETDRS LogMAR visual acuity test at a 4-meter distance over the test eye only under the following conditions:
 
 • dim illumination (e.g., <2.5 lux), low luminance, with high contrast charts (LLHC) • bright illumination (e.g., >400 lux), high luminance with low contrast charts (HLLC) 
The Precision Vision 4-meter high contrast ETDRS charts (Chart 1 and Chart 2 OD, Chart 3 and Chart 4 OS) and low contrast ETDRS charts (Chart 1 and 2 OD and Chart 3 and Chart 4 OS) will be used.
 
Two measurements per condition will be performed
	
2.8.	Subjective Lens Fit Assessment	
Evaluate overall lens fit acceptance (acceptable or unacceptable) based on centration, movement and other fitting characteristics.
 
An unacceptable fit is deemed by one of the following criteria:
 
 • limbal exposure at primary gaze or with extreme eye movement • edge lift • excessive movement in primary and up gaze • insufficient movement in all three of the following conditions: primary gaze, up gaze, and Josephson push up 	

Visit 2: Treatment 1 Follow-Up Visit		
Step	Procedure	Details
		Note: if lens fit is unacceptable subject will be discontinued from the study.
2.9.	Wettability Characteristics	Record the white light lens wettability of both lenses.
2.10.	Surface Deposits	Record any front and back surface lens deposits.
2.11.	Lens Damage	Using the slit lamp, assess lenses for damage.
2.12.	Lens Removal	
The lenses will be removed and stored in the following manner:
 
The OD and OS lenses will be stored wet (using saline solution) in separate glass vials with labels that minimally contain study number, date, subject number, and eye from which the lens was removed.
 
*The lenses will be shipped back to the Sponsor ambiently once the study has completed.

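### The acuity endpoint is defined under high luminance and high contrast, but the follow-up ETDRS steps list only the two mixed conditions (LLHC and HLLC)

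*Combined protocol and SAP*

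**What the plan says.** Protocol section 2.2 (Visual performance) defines the endpoint as distance acuity in each eye separately, with the study lens on, in logMAR from ETDRS charts at the 1-week follow-up. On the test condition it says: "This will be evaluated under high luminance and high contrast conditions at 4 meters".

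Section 4.3 shows which visits those are. Visit 2 is labelled "1-Week Follow-Up Visit with first pair of study lenses/Dispensing Visit Treatment #2" and Visit 4 "1-Week Follow-up Visit with second pair of study lenses and study exit".

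In section 7.2, the ETDRS steps at those visits (2.7 and 4.7) give two conditions:

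- "dim illumination (e.g., <2.5 lux), low luminance, with high contrast charts (LLHC")
- "bright illumination (e.g., >400 lux), high luminance with low contrast charts (HLLC")

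Step 2.7 adds "Two measurements per condition will be performed", and 4.7 says the same. For high contrast it allots two charts to each eye: "The Precision Vision 4-meter high contrast ETDRS charts (Chart 1 and Chart 2 OD, Chart 3 and Chart 4 OS"). The low-contrast charts are divided the same way. The dispensing-visit steps 1.23 and 3.18 list the same two conditions.

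Section 2.3 sets a non-inferiority margin of 0.05 logMAR for this endpoint, and section 14.6 tests it. Neither names a luminance or contrast condition. Nor does the ETDRS row of Table 4 in section 7.1.

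**The concern.** An endpoint definition and the procedure that collects it should describe the same measurement. Here the definition asks for bright light and high-contrast charts together. LLHC has the high contrast but not the high luminance, and HLLC has the high luminance but not the high contrast.

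If sites follow the steps, the 0.05 logMAR comparison must be run on a condition that 2.2 does not name. Section 14.1 promises a stand-alone SAP before the interim analysis. That document could choose LLHC or HLLC, but it cannot supply a reading that was not taken. A late choice between two measured conditions would also be open to challenge, because section 5.2 gives the interim biostatistician the decode.

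This is one of only two secondary endpoints, and it carries a formal hypothesis. It also bears on the study's purpose: section 1 suggests that the new mold process may improve optical quality.

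**Working it through.** There is no stated sample size or power figure to reproduce on this point. Table 6 covers the CLUE scores only. The check sets the definition beside the steps and counts readings.

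**Step 1. Match each condition to the definition.**

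| Source | Luminance | Contrast | Meets 2.2? |
|---|---|---|---|
| Endpoint, 2.2 | high | high | (definition) |
| Steps 2.7 and 4.7, LLHC | low | high | no, contrast only |
| Steps 2.7 and 4.7, HLLC | high | low | no, luminance only |

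**Step 2. Count readings at the endpoint visits.** This takes the two measurements per condition as per eye. The allocation of two charts to each eye at each contrast supports that.

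- Per eye per visit: 2 conditions × 2 measurements = 4 readings, of which 0 are high luminance with high contrast.
- Over Visits 2 and 4: 2 × 4 = 8 readings per eye, of which 0 qualify.

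The steps also speak of testing a single test eye, although lenses are worn bilaterally. If only one eye is tested, or if the two measurements are one per eye, the denominator changes. The numerator stays 0.

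**Step 3. Look for another source of the reading.**

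- The other follow-up acuity with the study lenses on is step 2.6, "Record the distance Snellen visual acuity with the contact lenses (OD, OS, and OU) to the nearest letter". Step 4.6 reads the same. It is Snellen, and the endpoint calls for ETDRS logMAR.
- Table 4, 2.3 and 14.6 name no condition.
- Appendix D lists an ETDRS procedure and a procedure for chart luminance and room illumination. Both are redacted and cannot be checked.

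**Step 4. Check whether the dispensing readings matter.** Section 14.6 puts a baseline covariate in the acuity model. In Table 4 the ETDRS row is blank in both Baseline columns and marked only at dispensing and follow-up. Steps 1.23 and 3.18 are therefore the only scheduled ETDRS readings before the week of wear. They are natural candidates for the covariate, but the documents do not say which reading is used.

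**Step 5. Size the option of adding a reading.**

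- Readings per eye per visit: 4 + 2 = 6.
- High-contrast readings per eye per visit: 2 (LLHC) + 2 (added) = 4, on 2 charts. Each chart is used 4 / 2 = 2 times. At present 2 readings on 2 charts implies one use each.
- Over the four ETDRS steps: 4 × 2 = 8 extra readings per eye.

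**The case against.** The strongest reply concerns reach. This is a secondary endpoint. Section 2.3 makes the primary objective depend on the two CLUE hypotheses alone, and the stopping rules in 14.8 contain no acuity criterion. That stands, and it limits the weight of the point.

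A second reply is that the redacted Appendix D procedures may call for the missing reading. That is possible. A reader might infer that a bright, high-contrast reading will never be taken in this trial, but the documents do not support going that far. They support only that the visit steps as written do not schedule one. An appendix that added it would still leave the steps incomplete.

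Third, the sentence in 2.2 could be stretched to mean two separate conditions, one of high luminance and one of high contrast. The plain reading is one joint condition. Even on the stretched reading, 14.6 has a single mean difference and a single margin, with no rule for choosing or combining LLHC and HLLC.

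Two further inferences are tempting:

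- *That the dispensing steps are irrelevant because the endpoint is read at follow-up.* The baseline covariate in 14.6 prevents that conclusion. The opposite claim, that 1.23 and 3.18 definitely supply the covariate, is not supported either.
- *That naming LLHC or HLLC in 2.2 is a mere wording change.* It changes the quantity tested. The documents give no rationale for 0.05 logMAR under any particular condition.

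**Conclusion.** The plan is wrong as written: the endpoint definition and the procedures that should collect it are inconsistent. By the visit steps, none of the follow-up ETDRS readings is in the condition that 2.2 defines. The zero does not depend on how the steps are read. The figures of 4 per eye per visit and 8 per eye over both visits assume that the repeat measurements are per eye.

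The conclusion is confined to the readable text, since the two Appendix D procedures could not be checked. It affects one of two secondary endpoints and its non-inferiority test. It does not touch the co-primary endpoints or the stopping rules, and it does not make acuity unanalysable: LLHC and HLLC data would exist, but not for the endpoint as defined. It should be fixed.

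**What to change.** Reconcile section 2.2 with steps 1.23, 2.7, 3.18 and 4.7, by one of two routes.

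**Preferred.** Redefine the endpoint in 2.2 and 14.6 as one named condition that is already measured, LLHC or HLLC. Do this before the SAP is finalised and before the interim decode is accessed. Confirm in the same change that the 0.05 logMAR margin applies to that condition. This adds no measurements. The downside is that the tested quantity is no longer the one now defined.

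**Alternative.** Keep 2.2 and add a reading of the high-contrast charts, under the bright illumination already required, at all four ETDRS steps. This must be in place before the first dispensing visit. Visit 2 falls 5 to 9 days after Visit 1, so a subject dispensed before the change could have a follow-up reading in the defined condition without a Visit 1 reading to match. The cost is two more readings per eye per visit, and each high-contrast chart shown twice to the same eye at a visit unless other charts are supplied.

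Under either route, 14.6 should state which reading serves as the baseline covariate for acuity.
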